## **Lay Summary**

We have made a new website called 'Active Brains' which aims to help older adults to look after their brain and body health. The aim is to help prevent problems with things like remembering, concentrating or reasoning (known as cognitive decline). The website will help older adults to make simple changes such as getting more active, playing brain training games and finding ways to eat more healthily.

This research will test how well the website works. We will be testing the website in two groups of people: 1) older adults with signs of cognitive decline, 2) older adults without any cognitive decline. Members of both these groups of people will be randomly put into one of three study groups: 1) care as they usually receive it from their GP practice, or 2) the Active Brains website, or 3) the Active Brains website plus a bit of support from a trained person (over the phone or by email). The study will last for five years. At the end of the first year we will compare people's thinking (cognitive) skills in each of the three study groups. After five years we will compare the three study groups again and also check how many of the people in each study group went on to be diagnosed with dementia.

The findings of this study will mean that we can tell whether the Active Brains website helps the people who use it to avoid or delay cognitive decline.

# **Background**

The prevalence of dementia is estimated to be between five and seven percent amongst those aged over 65 [1, 2] and although it has fallen slightly in the UK over the past 20 years [2] the absolute number of cases is likely to increase due to people living longer [3]. Over the next 30 years [3] 10-15 million cases are predicted in Europe, and more than 100 million in the world by 2050 [3, 4], with approximately 43% of prevalent cases needing high level care (equivalent to nursing home care)[3]. It has been estimated that if interventions could delay both disease onset and progression by a modest 1 year, there would be nearly 9.2 million fewer worldwide cases of the disease in 2050, with nearly the entire decline attributable to decreases in persons needing a high level of care [3].

Cognitive impairment in the absence of dementia is more common, but prevalence estimates vary considerably depending on definitions [5]. Mild Cognitive Impairment (MCI) is the most commonly used definition, conventionally defined as a deterioration in at least one non-memory cognitive domain in addition to memory impairment, without severe functional

impairment or loss of instrumental activities of daily living [5, 6]. The incidence of MCI is high in the over 65s [7-9] ranging from 51 to 76.8 per 1,000 person-years. There is no good evidence yet that screening for MCI is either effective or cost-effective [10], but a systematic review of cohort studies suggests that between 5 and 10% of MCI cases convert to dementia annually [11]. However, defining cognitive impairment solely in terms of MCI misses a large group of individuals who are at similar risk of developing dementia [12-14]. An alternative way of characterising cognitive impairment is Age Associated Cognitive Decline (AACD). AACD is defined as one standard deviation (SD) below normal cognitive functioning in any cognitive domain, with some investigators having an additional criterion (self-report of a gradual decline in memory present for at least 6 months) [5]. The estimated prevalence of AACD depends on how many cognitive domains are assessed, and whether additional criteria are used, which may explain the variable prevalence estimates – up to 20% of those aged over 60 in one population based study (additional criteria not used) [14], and lower in the UK Cognitive Functioning and Ageing Studies (additional criteria used: 2%) [5]. Progression to dementia is common whatever definition is used - with rates of conversion to dementia not much less than with MCI: 9% per annum in a population based study (additional criterion not used) [14], and 10% in Cognitive Functioning and Ageing Studies (additional criterion used) [12, 13]. Importantly, there is currently no diagnostic or treatment pathway for people with AACD. Given the scale of the problem, there are clearly insufficient resources currently on offer to help prevent cognitive decline or dementia in those with cognitive impairment, nor to prevent the development of cognitive impairment.

## What could help prevent cognitive decline or dementia?

It's now widely recognised that proactive management of modifiable risk factors can either delay onset or slow progression of dementia [15]. There is mounting evidence that healthy behaviour change (particularly physical activity) and cognitive exercises improve cognitive functioning and activities of daily living, and a recent trial from other settings has demonstrated the potential effectiveness of combining healthy behaviour and cognitive interventions [16].

Healthy behaviours: Physical Activity and Healthy Eating

Several large cohort studies and systematic reviews indicate that leisure time physical activity even at moderate levels is protective, as are fish and fruit and vegetables, with increased risks shown for obesity and saturated fat intake [17-23]. The Caerphilly cohort is representative of the UK population and measured proposed protective factors (non-smoking; healthy BMI; fruit/vegetable intake; physical activity; moderate alcohol intake [23]) and after 30 years demonstrated markedly reduced risks of cognitive impairment (odds ratio

(OR) for having four to five protective risk factors = 0.36, and of dementia OR = 0.36). A trial of the Mediterranean diet over four years demonstrated beneficial effects on cognitive decline among those with no cognitive deficits at baseline: changes in cognitive z-scores were 0.04 (-0.09 to 0.18) for the Mediterranean diet plus olive oil, 0.09 (-0.05 to 0.23 vs controls) for the Mediterranean diet plus nuts, and - 0.17 (-0.32 to -0.01) for the control diet [24]. Physical activity is protective in the shorter term [25] with effects even at six months to a year on both cognitive decline, grey matter volume and atrophy [26-28]. The Population Attributable Risk (PAR) has been estimated for diabetes, hypertension, obesity, physical inactivity, depression, smoking, and low educational attainment, and the highest PAR was for physical inactivity (21.8%, 6.1–37.7) [29].

#### Cognitive exercises.

A systematic review of cognitive exercise trials [30] documented a strong effect size in cognitive performance (weighted mean difference (WMD) = 1.07, confidence interval (CI): 0.32–1.83, n = 3,194) with effects maintained after two years. A more recent systematic review of cognitive and memory training among those with MCI documented substantial heterogeneity of interventions [31], but a promising effect of cognitive exercises (effect sizes ranging from .10 to 1.21). The large ACTIVE study investigated the effect of training in several cognitive domains (memory, reasoning, speed of processing) [32]; the change in reasoning (effect size 0.26) was particularly important, resulting in significantly less functional decline in activities of daily living which was maintained over five years. Booster training produced additional improvement for reasoning performance (effect size 0.28) [32].

### Feasibility of online delivery

Whilst there is good evidence that healthy behaviour changes can be protective against cognitive decline, behavioural interventions are complex and resource intensive if delivered by purely face-to-face methods. In contrast, the internet is now used extensively and successfully by older people for self-management [33, 34]. Although many individuals may benefit from a free standing intervention (without additional support), the additional impact of behavioural facilitation may be important in helping initiate and maintain behaviour change [35, 36] - and the effectiveness and cost-effectiveness of a more intensive intervention may vary with the risk of developing dementia.

#### Internet use amongst older adults

Recent UK government statistics demonstrate that the proportion of older adults using the internet is rapidly increasing. Amongst 55-64 year olds, 88.3% reported recent (in past three months) internet use. Between 2011 and 2016, the proportion of adults aged 75 and over

reporting recent internet use nearly doubled [37]. Although this proportion of frequent internet-users declines across age groups, this latter age-group have demonstrated the fastest growth.

The research team has extensive experience of ensuring intervention engagement and accessibility to encompass a range of user preferences [38] and have experience of successfully supporting older patients e.g. exercises for dizziness [39] and rehabilitation for stroke, and falls prevention [40]. The team can also draw upon existing experience of developing suitable interventions to ensure engagement and accessibility for people of all ages and computer abilities and lower health literacy [38, 41].

Internet delivered cognitive training amongst a cognitively impaired population

A large trial (n=2912) led by one of the research team's coinvestigators (CB) used an online cognitive training package in our target populations (ReaCT: Reasoning Cognitive Training package) with improvements after six months in Instrumental Activities of Daily Living, reasoning and verbal learning (standardised effect sizes respectively of 0.15, 0.42, and 0.18). There were very similar effect sizes among those with Age Associated Cognitive Decline (AACD). This suggests that a web based package is likely to be feasible and effective among those with cognitive decline. Although currently some of our target population are not internet users this proportion is rapidly declining [37], and so the findings of this study will be relevant to the large majority of the older population in future.

## Intervening with non-cognitively impaired older adults

Intervening with non-cognitively impaired older adults may also prevent dementia. Whilst an intervention for non-cognitively impaired older adults may be expected to have a smaller effect, data from the above-mentioned large ReaCT trial led by CB suggests that this is not necessarily the case. Furthermore, the non-cognitively impaired are a substantially larger proportion of the population, so an intervention to target this group provides potential for many more of the older age population to be helped. The older age population are also very concerned about developing dementia: 80% of those aged 50 or more in a survey undertaken by Saga (n=9049) said they feared dementia, which was equivalent to fear of cancer, and 84% feared dementia in their partners, which was more than they feared cancer in their partners [42]. Fear of dementia, the need to improve dementia knowledge, and having adequate support for behavioural change rather than simply being told what to do are likely to be major motivators towards changing health behaviours in an older age general population group [43]. Thus it is plausible that a well-designed and engaging behavioural intervention to help prevent cognitive decline and dementia will be both well-received, and

effective, among an older age general population sample, and will be strongly supported by their partners.

# Study aims and outcome measures

The primary aim of this study is to assess the effectiveness and cost-effectiveness of a digital intervention (Active Brains) to help support older adults (60-85 years) with and without cognitive impairment in making healthy changes (physical activity, brain training, diet) to maintain cognitive function and prevent cognitive decline.

## **Primary Research Objective:**

Amongst older adults (60-85 years) both with and without cognitive impairment, the primary research objectives are:

- to estimate the effectiveness and cost-effectiveness of the Active Brains digital intervention (compared with usual care) in maintaining cognitive functioning (assessed by verbal reasoning performance).
- 2) to estimate the effectiveness and cost-effectiveness of the Active Brains digital intervention (compared with usual care) in maintaining cognitive functioning (assessed by verbal reasoning performance) when supported as necessary by a trained behavioural facilitator.

The primary outcome (effectiveness) measure at one year is an online version of the Baddeley Verbal Reasoning task.

At the five year follow-up point\*, a further primary objective is to estimate the effectiveness of the Active Brains digital intervention in delaying dementia. This will be determined in the following way:

1. If there is a notes diagnosis of dementia participants will be classed as having dementia.

As recording in notes is often sub-optimal, as sensitivity analyses, we will use the following methods to ascertain the dementia outcome:

- 2. Self-report item "Has a doctor or other medical worker ever said that you have dementia?" (Y/N) as collected in baseline and year 1 and year 5 follow-up online/paper measures.
- 3. Evidence of significant decline in Baddeley (baseline to follow-up) **AND** evidence of functional deterioration (EITHER: a) significant change in self-report IQCODE (baseline to

follow-up) OR b) two self-report questions on difficulty in finance and planning\*. These items are collected in year 5 online/paper measures.

\* The items are:

Thinking about how you were ten years ago, how are you at:

- a) handling your personal finances (banking, pension, etc)?
- b) thinking about future events and planning ahead?

(Much improved/ A bit improved/ Not much change/ A bit worse/ Much worse)

Self-completed IQCODE will be used as it is likely to provide the most complete data. However, we will also explore the agreement between self-completed IQCODE and informant completed IQCODE among willing contacts (where provided), how these relate to other outcomes, and the implications of using self-completed or informant completed measures.

We will also explore the implications of using decrements in the other computerised tests (spatial working memory, attention, and verbal short-term memory) combined with IQCODE in indicating a diagnosis of dementia.

4. Self-report of difficulty in finance and planning alone.

## **Secondary Research Objectives:**

A key secondary research objective is to measure differences across trial arms in the change in the proportions of participants to a different category – either from no cognitive impairment to cognitive impairment (AACD or MCI), from AACD to MCI or severe cognitive impairment, or from MCI to severe cognitive impairment. The Baddeley verbal reasoning task will be used to indicate AACD (defined as scores more than 1 SD below the normative score\*),MCI (defined as scores more than 1.5 SD below the normative score\*) or severe cognitive impairment (defined as scores more than 2 SD below the normative score\*). These are study specific definitions rather than formal diagnostic criteria.

\*normative score determined by PROTECT database – large (n>15,000) cohort of older adults' data on battery of cognitive assessment tasks (https://www.protectstudy.org.uk/)

Additional secondary research objectives are to evaluate the effectiveness of the Active Brains digital intervention across a number of other key outcomes:

- 1. Instrumental Activities of Daily Living
- 2. Additional cognitive outcomes (including spatial working memory, attention, and verbal short-term memory)

\* Funding for five year follow-up is contingent on evidence of effectiveness in changing behaviour and improving cognition at 1 year.

- 3. Health-related quality of life
- 4. Patient enablement
- 5. Depression
- 6. Changes in the target behaviours (physical activity (including sedentary time), healthy eating, engagement with brain training games)
- 7. Mortality data

A complete list of measures is provided in table 2 at the end of the document.

# Study design

Fully powered, definitive trials will test the effectiveness and cost-effectiveness of both the standalone Active Brains digital intervention and the Active Brains digital intervention plus support from a central facilitator to see if either of these interventions can maintain cognitive function and prevent cognitive decline (compared with usual care), in two groups of people:

1) older people who currently show signs of MCI or AACD, 2) older people who do not show any signs of cognitive decline.

Participants will be randomly allocated to one of three study groups:

- 1. Usual care
- 2. Access to the Active Brains website
- 3. Access to the Active Brains website with flexible human support from a central support facilitator

There are therefore two parallel trials with the same trial interventions: in one trial we will be recruiting a group of patients with cognitive decline and in the second trial a group without cognitive decline.

### Sample Size Calculations

### Cognitive decline trial

## **Baddeley reasoning test (Primary outcome)**

We initially proposed an alpha of 0.025 for the primary outcome to adjust for multiplicity. However, where there are independent comparisons with control it is not mandatory to allow for multiplicity, as is currently the case with a host of platform trials and multi-drug trials which use a common control group - but where intervention groups are then compared as secondary comparisons multiplicity concerns become more important [44-46]. To make our approach consistent between outcomes we therefore assumed an alpha of 0.05 for

comparisons between each intervention group and control with the agreement of both the TSC and the funder. For the primary outcome of cognitive decline for 80% power to detect a standardised effect of 0.15 requires 698 per group for the MCI subgroup and the same again for the AACD subgroup or 4188 in total. Since the limiting factor in the sample size calculation is for the dementia outcome, the total sample size will provide more power for the primary outcome.

## For primary outcome at one-year follow-up:

Assuming that 70% will be available to provide follow-up at 1 year, we will need 5983 in total.

#### For primary outcome at five-year follow-up:

Assuming that 60% will be available to provide follow-up within 5 years, this rises to 6980 in total.

#### Progression to dementia

Although the reduction in cognitive decline as assessed using the Baddeley reasoning test is the primary outcome at one-year, the limiting factor in the sample size calculation for those with cognitive impairment is the progression to dementia at five-years. We assume a 5% annual progression rate to dementia among those who are cognitively impaired. With alpha 0.05 and 80% power, we aim to detect a difference of 5% after 5 years (20% intervention and 25% control) in those with dementia (estimated as specified on pages 10-11). This means we would need 1094 in each of the MCI and AACD groups or a total of 2188. Assuming that 60% will be available to provide follow up in 5 years requires 3647 in each of the 3 study groups or 10940 in total.

### Non-cognitive decline trial

Baddeley reasoning test (Primary outcome)

We assume few of those who have no cognitive impairment at baseline will develop dementia, and that we might find a smaller effect of the intervention. For the primary outcome of cognitive decline we assume an alpha of 0.05 and 90% power to detect a standardised mean difference of 0.1 in the Baddeley. This requires 2103 per group.

#### For primary outcome at one-year follow-up:

Assuming that 70% will be available to provide follow-up at 1 year, we will need 3004 per group, or 9013 in total.

#### For primary outcome at five-year follow-up:

Assuming that 60% will be available to provide follow-up within 5 years, that rises to 3505 per group or 10,515 in total.

- Therefore, in order to be powered to detect an effect at 5 year follow-up: In patients
   with cognitive decline we will recruit a minimum of 3647 patients to each of the three
   study groups (10,940 total); there will be a mixture of patients with MCI and AACD.
- In patients without cognitive decline we will recruit a minimum of 3505 patients to each of the three study groups (10,515 total).

This means our total sample size across both trials will be a minimum of 21,455 participants in the trials. Should we not continue to five-year follow-up (see page 10), we should have sufficient power to detect an effect at one year follow-up when we have recruited n=7260 into the cognitively impaired trial, and n=9013 into the cognitively healthy trial; or total sample size of n=16,273. Since the interventions are identical in both trials we will not only be able to analyse the two trials separately but also as a combined data set. These calculations are summarised in Table 1.

Table 1. Summary of sample size calculations for each trial and outcome

Cognitive dec	line trial	Number of MCI/AACD participants per trial arm required		Total number of participants per trial arm	Total
Primary outcome measures	Cognitive Decline – Baddeley Verbal reasoning (alpha = 0.05, 80% power to detect standardised mean difference of 0.15 in Baddeley)	698 of each		1396	4188
	Progression to Dementia at 5 years (Assuming 5% progression rate – alpha = 0.05, 80% power to detect 5% diff after 5 years)	1094 of each		2188	6564
		For 1 Year Fol	low-up		

Baddeley ve	997 of 6	each		1994	5983					
accuming i		For 5 Ye	ar Fol	low-up		L				
Baddeley Verbal reasoning - 1163				•	6980					
assuming 60% follow up each										
	ı to dementia –	182			3647	10940				
assuming 6	0% follow-up	of ea	ıch							
Non-cogniti			Total numbe	Total						
				participants per trial arm						
	Cognitive Decline	_		2103	6309					
Primary	Baddeley Verbal									
outcome	reasoning (alpha =									
measure	90% power to detec	t								
	standardised mean									
	difference of 0.1 in									
	Baddeley)	For 1 Ye	ar Fol	low-up						
Baddeley verbal reasoning - assuming			 	3005	9013					
70% follow-up				0000		2210				
		For 5 Ye	ar Fol	low-up						
Baddeley Verbal reasoning – assuming 60% follow up				3505		10515				

Our ongoing feasibility trial (REC reference 18/NW/0341) has so far demonstrated that our proposed recruitment, screening and randomisation procedures have proven feasible and allowed us to recruit to target (n=360) within a three-month time frame (as planned). Furthermore, study recruitment materials proved accessible and acceptable amongst our participants.

# Study participants

### Identification and non-participation

Participants will be recruited via Primary Care. Recruitment will involve practice staff inviting patients from practice lists (GPs will screen practice lists to avoid inviting those who have an existing diagnosis of dementia, are terminally ill, seriously mentally ill or have/had long-COVID). Invitation letters, participant information sheets, and a 'getting started' sheet with instructions on how to log on to the website to start the study, will be sent from GP Practices. Reply slips (for those not interested to inform us why) will be included in these mail out packs for 5% of participating practices. Prospective participants can also contact the research team directly if they have any questions. GP practices will be asked to provide demographic data (gender and age) for all participants who are invited to the study. A subsample of practices will also be asked to provide Index of Multiple Deprivation (IMD)

anonymised data for all participants invited to the study. We will compare demographics and IMD data of those invited who do not participate to recruited participants to examine any differences between these two groups. This will help us to assess the likely generalisability of our findings.

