## **Eligibility Criteria**

When patients first register on the Active Brains study website they will answer a series of screening questions to make sure that they fit the study inclusion criteria below. Figure 1 outlines the participant identification and screening procedures.

To be eligible for inclusion, individuals with signs of cognitive decline will:

- Be aged between 60 and 85 years old inclusive
- Have cognitive impairment (AACD) defined as 1 SD below the norm on the Baddeley reasoning test [47]. A key subgroup is MCI, which will be defined simply as 1.5 SD below the norm on the Baddeley reasoning test. In statistical analysis we will also explore the impact in subgroups defined by alternative combinations of impairment in Baddeley reasoning, IADL and memory e.g. of MCI defined as 1.5SD below the norm in another non-memory cognitive domain plus memory impairment [5, 12, 13], and AACD defined as 1 SD below the norm for the Baddeley reasoning test [47] and IADL.
- Be willing and able to access the internet
- Not have an existing diagnosis of dementia at baseline
- Not report high levels of leisure time physical activity already (i.e. score 30 or more on the Godin Leisure Time Exercise Questionnaire (counting moderate or vigorous physical activity only)).
- Will not have a recorded diagnosis of long-COVID in their medical records at baseline

To be eligible for inclusion individuals without signs of cognitive decline will:

- Be aged between 60 and 85 years old inclusive
- Have normal cognitive function (i.e. do not meet criteria for cognitive impairment as defined above)
- Be willing and able to access the internet
- Not have an existing diagnosis of dementia at baseline

- Not report high levels of leisure time physical activity already (i.e. score 30 or more on the Godin Leisure Time Exercise Questionnaire (counting moderate or vigorous physical activity only)).
- Will not have a recorded diagnosis of long-COVID in their medical records at baseline

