#### Randomisation

Patients will be randomised online using the study software. They will have an equal chance of being in each of the three groups in each of the two trials (the trial among those with cognitive impairment, and the trial among those with no cognitive impairment). Once randomised, participants will be informed of their group allocation (they will also be emailed this information). If participants are in one of the treatment arms they will be taken directly to Active Brains where they can begin the intervention. These participants can then use Active Brains as much as they would like to over the course of the study. The central facilitator will be notified by email when a participant is randomised to the support arm of the trial, so that they know to expect to provide support to the participant in the coming weeks.

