opportunity to participate in a non-randomised cohort study which will provide the same digital intervention as in the full trial, with online self-completion of follow up only (we won't do a notes review or provide additional support from a centralised facilitator to this group). Whilst we don't expect it to be the case, in the unlikely event that we reach our recruitment target for the cognitively impaired trial first (n = 10,940), any additional individuals beyond this target would enter the cohort study. This would be instead of the cohort group being populated by over-recruitment from the non-cognitively impaired trial (which we think is more likely). After initial screening indicates that these participants are eligible, and that they are not needed for the randomised trial, these participants will be shown a different participant information sheet for a cohort study online and will complete a slightly different consent form. This procedure could be beneficial for participants without signs of impairment who will get access to the Active Brains intervention and will enable us to examine how the intervention might be implemented outside of a randomised trial (which will be more similar to the effects one might expect if implementing in clinical practice).

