#### 2.3 Randomisation details

Patients will be randomised online using the study software, which performs simple randomisation and concealment. Once randomised, participants will be informed of their group allocation (they will also be emailed this information). If participants are in one of the treatment arms they will be taken directly to Active Brains where they can begin the intervention. The participants, supporters and study team are unblinded, but the statistician will remain blinded.

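### With no household rule in the trials or the cohort, a usual-care participant can live with an Active Brains user, and no planned analysis would show it

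*Protocol*

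**What the plan says.** **Invitation and eligibility.** Under Identification and non-participation, the Protocol states: "Recruitment will involve practice staff inviting patients from practice lists". GPs first screen out dementia, terminal illness, serious mental illness and long-COVID. Both eligibility lists include "Be aged between 60 and 85 years old inclusive". Neither has a criterion about other members of the household.

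**Allocation.** The unit is the individual: "They will have an equal chance of being in each of the three groups in each of the two trials" (Protocol, Randomisation). SAP section 2.3 describes study software "which performs simple randomisation and concealment". Participants are told their arm at once.

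**Cohort.** Under Consent and Screening, once the non-decline trial reaches 10,515, further non-impaired registrants are offered "a non-randomised cohort study which will provide the same digital intervention as in the full trial". The Protocol thinks this order of filling more likely than the reverse. The offer does not depend on whether a household member is already in a trial.

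**Partners.** The Protocol's background (Intervening with non-cognitively impaired older adults) calls it plausible that the intervention "will be strongly supported by their partners".

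**Analysis.** The SAP has no household identifier, no clustering term and no analysis of exposure through a cohabitant. Section 4.4.2 defines adherence by the participant's own use and behaviour. Section 4.2 says only that control-group use of other websites is not a deviation. The sample size text in both documents makes no allowance for contamination.

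**The concern.** Two members of one household can enrol by two routes. Both may be randomised, in which case the housemate of a usual-care participant has a 2/3 chance of an Active Brains arm. Or one may be in usual care while the other is given the website in the cohort, where access is certain. Diet, activity and breaks from sitting are targets of the intervention and are easily shared at home.

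The effects sought are small: 0.1 SD in the non-decline trial, and 0.15 SD and 25% versus 20% dementia in the decline trial. A modest gain in usual care would use up part of them. Five-year follow-up also depends on evidence of effectiveness at one year (SAP section 2.4), and as written no planned analysis could separate household sharing from a weak intervention.

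**Working it through.** **1. The plan's own sizes (two-sided alpha 0.05).**
- Non-decline trial, "we assume an alpha of 0.05 and 90% power to detect a standardised mean difference of 0.1 in the Baddeley": 2 × (1.960 + 1.282)² / 0.1² gives 2,102 per group; the plan states 2,103.
- Decline trial, Baddeley, "for 80% power to detect a standardised effect of 0.15 requires 698 per group for the MCI subgroup": 2 × (1.960 + 0.842)² / 0.15² gives 698, as stated.
- Dementia, 25% versus 20%, 80% power: 1,094 per group in each subgroup, as stated.
- At 60% follow-up: 3 × 2,103 / 0.6 = 10,515 and 3 × 2,188 / 0.6 = 10,940, as stated.

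The stated sizes therefore reproduce with no margin for dilution.

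**2. Dilution model.** Diluted effect = planned effect × (1 − h × e × s).
- h is the share of usual-care participants with a co-registering partner. *Assumed*: 10–30%.
- e is the chance that such a partner has the website (step 3).
- s is the share of the effect passed to a usual-care housemate, over and above any gain to a housemate already in an Active Brains arm. *Assumed*: 25–75%.

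For dementia, the control risk becomes 25% − 5% × (h × e × s).

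**3. Exposure, e.**
- Non-decline trial: e = 2/3, taking the partner as also randomised.
- Decline trial: assume normal scores, so 15.9% fall below −1 SD, and a constant mix of registrants. The non-decline trial fills after 10,515 / 0.841, about 12,500 registrants. The decline trial needs 10,940 / 0.159, about 69,000. So 1 − 12,500/69,000 = 82% of it is recruited while the cohort is open, and e = 0.82 × (0.841 + 0.159 × 2/3) + 0.18 × 2/3 = 0.90.
- If 30% are classed as decline, that share is 1 − 15,021/36,467 = 59% and e is about 0.80.
- Both values assume that every surplus partner accepts the cohort and that partners' impairment is independent.

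**4. Power.** The decline-trial columns use e = 0.90.

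| h, s | Effect lost, non-decline | Baddeley, 5 years (2,103 per arm) | Baddeley, 1 year (0.7 × 3,505 per arm) | Effect lost, decline | Dementia, per subgroup (1,094) | Dementia, whole arm (2,188) |
|---|---|---|---|---|---|---|
| none | 0 | 90% | 94% | 0 | 80% | 98% |
| 10%, 25% | 1.7% | 89% | 93% | 2.2% | 78% | 97% |
| 20%, 50% | 6.7% | 86% | 90% | 9.0% | 73% | 95% |
| 30%, 75% | 15% | 79% | 85% | 20% | 62% | 89% |

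Five-year Baddeley power in the non-decline trial drops below 80% once about 13.7% of the effect is lost. Whole-arm Baddeley power in the decline trial at five years stays near 98% or higher in every row. The one-year column assumes recruitment to the five-year target. If recruitment stopped at the 9,013 given for one year, about 2,103 per arm would be followed up and the five-year column would apply.

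**The case against.** The strongest reply is that the drivers are all assumed. No passage gives a co-enrolment or spill-over rate. At 5% co-enrolment and 25% spill-over among randomised pairs, non-decline power moves only from 90% to 89.5%. Brain training and facilitator calls are aimed at the individual participant, so large spill-over on a verbal reasoning test is far from given. Usual care already receives brief advice on activity, diet and staying mentally active. All of this stands, and it limits the point to a missing safeguard of unknown size.

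The per-subgroup dementia figures also look worse than the primary analysis would. SAP section 3.1 analyses each trial as a whole, and section 4.4.1 handles MCI by an interaction term. Whole-arm power is then the relevant figure, and it holds up well. The subgroup figures matter only because the plan sized the decline trial on them.

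Four stronger readings are tempting and not supported:
- *That whole lists, and so both members of every couple, are invited.* The Protocol says only that invitations come from practice lists after GP screening. Nothing prevents both being invited, but nothing says both are. Figure 1 is not available.
- *That every contrast is biased toward no effect.* Intervention-arm participants have co-enrolled partners too. If a partner's use adds the same amount whatever one's own arm, the contrast is unchanged.
- *That most of the decline trial will be recruited while the cohort is open.* The Protocol says only which trial is likelier to fill first. The 82% and 59% follow from assumptions about scores and recruitment.
- *That restricting the analysis to sole-enrolled participants keeps the arms comparable.* Allocation is disclosed at once, so a partner may register because of it, for example to obtain the website after the first person drew usual care. Being the only enrolled member is then partly a post-randomisation variable.

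**Conclusion.** The gap is real and can be read directly from the text. Randomisation is individual, there is no household rule, the cohort can give the website to someone living with a usual-care participant, and no analysis would detect it. No stated figure is wrong.

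Dilution follows only if spill-over helps usual care more than the Active Brains arms. Under the assumed ranges, 2–15% of the effect is lost in the non-decline trial and 2–20% in the decline trial. The loss that touches a trial-wide primary comparison most is five-year Baddeley power in the non-decline trial, 90% to 79–89%. Dementia power falls to 62–78% per subgroup but stays at 89–97% for whole arms. At the low end the effect is minor. Any bias in the estimates would remain even where power is ample. The cohort route should be closed because doing so costs the trials nothing, and the remainder should be measured.

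**What to change.** 1. **Cohort offer (Protocol, Consent and Screening).** Ask at registration whether a household member is already in either trial. Do not offer the cohort to anyone who says yes, whatever that member's arm. *Cost:* one question and a somewhat smaller cohort; no trial participant is lost. It does not cover a cohort member whose partner joins a trial later, which item 2 would record.

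2. **Household flag and sensitivity analysis (SAP sections 4.1 and 4.6.2).** Flag shared households from the postcodes in Protocol Table 2 and the postal addresses held for reminders, and report co-enrolment by arm. Postal reminders go only to randomised participants, so cohort matches may rest on postcode and the new question.
   - Pre-specify a sensitivity analysis of the primary outcomes by household status fixed before randomisation, such as whether a household member was already enrolled.
   - In co-randomised pairs, use the partner's randomised arm to estimate spill-over. For the later enrollee, the contrast between own arms within each partner arm is protected by randomisation. Comparisons across partner arms are less secure, because joining may have depended on the partner's allocation.
   - Do not restrict to the only enrolled member as if that were independent of arm.
   - *Cost:* address matching and one added analysis, feasible even if enrolment is complete.

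3. **Optional: one participant per household within the randomised trials.** This leaves the required numbers unchanged, but it can turn away an impaired person whose partner registered first, and the decline trial has the larger target (10,940). The sponsor should weigh that loss before adopting it.
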